#### 5.4. Intervention and follow-up

The intervention and follow-up of participants will begin after the conditions eligible to participate in the study are verified, proceeding as follows:

5.4.1. For selected participants with pre-existing risk factors, these are: immediately previous pregnancy terminated prematurely with preterm birth, or premature rupture of membranes before 35 weeks of gestation; placement of a progesterone cerclage pessary, or treatment with progesterone capsules will start at week 16 (0/7) but not beyond 24 (0/7) weeks of gestation. These participants will have a transvaginal ultrasound performed to document the length ( $\geq 10$  mm) and position of the cervix at the placement of the pessary or the start of treatment with vaginal progesterone capsules.

5.4.2. For pregnant patients with a single fetus, selected for the presence of a shortened cervix (between 10 mm and 25 mm), the pessary will be inserted or the vaginal administration of progesterone capsules will be started at the time of the investigation, but not before 16 (0/7) weeks of gestation and not after 24 (0/7) weeks of gestation. The cervix angulation relative to the uterus body using the intersection of the uterus posterior wall longitudinal axis with the cervical canal axis in addition to a measurement of the cervical length will be performed on 60% of the study participants assigned to one of the two groups with medicated pessary, prior to insertion of the pessary and after its insertion, by means of a transvaginal ultrasound technique recently described (25). The transvaginal ultrasonography post-insertion of the pessaries may be performed at visit one or at visit two at the latest.

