5.4.3. After insertion of the pessary or beginning of the administration with vaginal progesterone capsules and until 28 weeks of gestation, participants in the 3 treatment groups will be monitored every 4 weeks at the most or more often, if the site has established so as a control standard. After 28 weeks, patients should be monitored every 2 weeks. At every control visit, procedures applicable to their prenatal control and a transvaginal ultrasound by standard technique will be performed (patients receiving vaginal capsules), if considered necessary by the physician, or transvaginal using the technique recently described (25) (in patients with medicated pessary) to measure and record cervical length. The occurrence of possible side effects, adherence to treatment, and visits or hospitalizations due to threat or preterm labor will also be recorded, as well as the existence of potential causes for *ex-post* exclusion from the study. In addition, concomitant medication will be recorded at each visit.

5.4.4 Management of participants consulting due to a threat or premature labor will be conducted according to the diagnostic and therapeutic guidelines of the Ministry of Health (MINSAL) (Clinical Guide for Preventing Preterm Birth - MINSAL 2010) and the respective hospital's Obstetrics and Gynecology Service. In these cases, the treating physician will be provided with information about the progesterone treatment the patient is receiving in the study, and the decision for her continuation in the clinical study will be made jointly as far as possible, since the opinion of the treating physician shall predominate.

5.4.5 Every case will be closed at 36 6/7 weeks of gestation, or at the time of preterm birth. Data on the birth, condition at birth, and evolution of infants born preterm will be analyzed, recording morbidity and mortality through the time of discharge from the hospital.

The participant's attending health team (physicians and midwives) will be informed in writing about the participation of these women in the study by means of an identification

card that will be given to every woman participating in the study. In the pregnancy card, participation of these subjects in the study will be emphasized by means of a self-adhesive sticker detailing their participation in one of the treatment groups (pessary or capsule) and recorded in the medical history.

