3. STUDY DESIGN

A phase II, efficacy, multicenter, controlled, open label, parallel and randomized exploratory clinical study. It will include singleton pregnant subjects, with history of premature birth and/or short neck and an increased risk of premature birth, who, after reading the informed consent, voluntarily accepted to participate in the study.

For the secondary outcomes, subjects will be their own controls on the following variables to assess: anatomical characteristics of the cervix – position and length; development of surveys in pregnant women to establish the acceptability and tolerance of the intervention; and aspects of local and systemic safety.

Two hundred and seventy +10% pregnant women with risk of premature birth will be enrolled at the participating sites. This population will be divided into 3 groups of treatment with 90 participants each, where control group (A) is with intravaginal capsule of micronized progesterone 200 mg, groups B and C are pessaries with 6.3 g and 7.7 g of sustained release progesterone respectively.

In the prenatal and/or ultrasound control between 16 and 24 weeks of gestation, they will be informed and invited to participate in the study. The inclusion of the volunteers will be in all cases until weeks 24 (0/0) of gestation. The volunteers will be selected on the basis of their clinical history and by trans-vaginal ultrasound performed between 16 and 24 weeks. All volunteers with unique pregnancy and cervical length ≤ 25 mm but ≥ 10 mm, will be invited to participate in the study. Prior to inclusion in the study, it is confirmed the vitality of the fetus or other exclusion criteria detailed later. Subjects who refuse to participate in the study will receive the current standard of care in each participating site, according to their condition.

EVALUATION VISITS

The study includes 8 visits to the site. The programmed schedule of assessments for its conduction and the activities to take place in each and one of them are specified in Table 1.

SAMPLE SIZE

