5. ANALYSIS CONVENTIONS

The statistical analysis will be made by ILS Clinical Research under the authorization of Laboratorio Andromaco S.A.

GENERAL PRINCIPLES

The statistical analysis will be provided to give a general summary of the study subjects and a vision of the efficacy and safety of the results. The data provided by the sites will be summarized for this purpose. Tables of absolute and relative frequencies will be constructed for the quality variables. All the percentages will be presented with a decimal. The quantitative variables will be summarized with the number of subjects participating (n), mean, standard deviation (SD), and median, maximal and minimal.

Two tailed test will be carried out for all the analysis and the type I error is 0.05 for continuous variables and the discrete variables. All p values shall be rounded to three decimal and the values under 0.001 will be presented as <0.001 and values greater than 0.999 will be presented as 1.000. A comparison of the treatment groups will be done with respect to the demographic and baseline characteristics using inferential statistical techniques to detect if any of these variables may condition the results in the dependent variables. Comparisons in qualitative variables will be carried out using the Cochran-Mantel-Haenszel (CMH) test of general association, while the comparisons in quantitative variables will be made with a test of comparison of means (ANOVA analysis of variance) for independent samples with normal distribution. In the cases of no normality on the continuous variables, or in case of not belonging to the exponential family for discrete data, the parametric tests will be replaced for nonparametric tests such as Kruskal-Wallis or Friedman. These tests will be presented in each table as deemed necessary. All confidence intervals will be two-tailed and at 95%.

Table 1: Study Schedule of Assessments

Activities	Visit 1	Visit 2	Visit 3	Visit 4	Visit 5	Visit 6	Visit 7	Final Visit
Demography	X							
Medical History	X							
Physical Exam	X	X	X	X	X	X	X	X
Gynecological Exam	X							
Vital Signs	X	X ¹	X ¹	X ¹	X ¹	X ¹	X ¹	X ¹
Transvaginal Ultrasound	X	X ²	X	X	X	X	X	X
Pre-birth Control	X							
Obstetric Background	X							
Lab Tests (Blood and Urine)	X							
Eligibility	X							
Vaginal Discharge	X	X ³	X ³	X ³	X ³	X ³	X ³	X ³
Randomization	X							
Pessary Insertion	X							
Acceptability and tolerance to the insertion	X							X
Concomitant Medications	X	X	X	X	X	X	X	X

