Occurrence of membranes' ruptures: Premature rupture of membranes after 32 weeks but before 34 weeks of gestation. The Cochran-Mantel-Haenszel (CMH) test will be used, where the incidence of rupture of membranes in each group will be compared and will be identified through the registration of adverse events.

Anatomical cervical changes (Only groups B and C): The length of the cervix and cervical angle variables, will be described as continuous and measured variables through time, using the test of comparison of means through the Analysis of Variance (ANOVA) for repeated measures, considering the baseline result as a covariate in the comparison and shall be based on the sum of squares type III. The difference between groups regarding the change from baseline will be assessed through t tests paired within ANOVA, utilizing the difference in means estimated by least squares. These comparisons will be made amongst all treatment groups with pessary.

Acceptability and tolerability of insertion (only groups B and C):

Acceptability and tolerability will be assessed through a questionnaire which must be completed at the beginning and end of the study. Questions (i) and (ii) are answered at visit 1, question iii (VAS) is answered at visit 1 and final visit, and questions (iv) to (ix) are answered at the final visit.

It is composed of several items

- (i) Ease of insertion (visit 1). This question has the following categories: 1 = very good, 2 = good, 3 = regular, 4 = bad and 5 = very bad; and only one of them will be selected.
- (ii) Subjects pain at the time of insertion (visit 1). This question has the following categories: 1 = without pain, 2 = with little pain, 3 = with moderate pain, 4 = with intense pain and 5 = with unbearable pain; and only one of them will be selected.

- (iii) Visual Analog Scale of pain (VAS) (visit 1 and final visit): this scale is evaluated in 10 points where 10 represents the worst pain suffered during her lifetime and 1 the absence of pain.

Analysis for the VAS will be described as continuous and measured variables through time using the test of comparison of means through the Analysis of Variance (ANOVA) and must be based on the sum of squares type III. The treatment differences regarding the change from baseline, will be assessed through t tests paired within ANOVA, utilizing the difference in means estimated by least squares. These comparisons will be made amongst all treatment groups.

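### The repeated-measures ANOVA of cervical length and angle states neither its time scale nor how incomplete series are handled; in its classical form it would drop early deliverers and late entrants

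*SAP*

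**What the plan says.** SAP Section 10, under the secondary analysis, treats cervical length and angle in groups B and C (the 6.3 g and 7.7 g pessaries) as continuous outcomes followed over time. Means are compared "using the test of comparison of means through the Analysis of Variance (ANOVA) for repeated measures". The plan adjusts for the starting value and fixes the type of test, "considering the baseline result as a covariate in the comparison and shall be based on the sum of squares type III". Group differences in change from baseline are then assessed by t tests, "utilizing the difference in means estimated by least squares".

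On timing:

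- SAP Section 3: "The study includes 8 visits to the site". Table 1 in SAP Section 5 marks "Transvaginal Ultrasound" at all eight (Visits 1 to 7 and the Final Visit) and gives no gestational-age windows.
- Protocol 5.4.2: for women with a short cervix, treatment starts "not before 16 (0/7) weeks of gestation and not after 24 (0/7) weeks of gestation". Protocol 5.4.1 sets the same limits for women with a risk history.
- Protocol 5.4.3: until 28 weeks, "participants in the 3 treatment groups will be monitored every 4 weeks at the most or more often"; then "After 28 weeks, patients should be monitored every 2 weeks".
- Protocol 5.4.5 closes each case at 36 6/7 weeks or at preterm birth. SAP Section 9 ends a woman's participation early if the pessary has to be removed.

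For this analysis neither document states the time variable, the covariance structure, the SAS procedure or a rule for incomplete series.

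**The concern.** A classical repeated-measures ANOVA has one row per woman and one column per occasion, and it discards any woman with an empty cell. In this trial empty cells are not random. Follow-up stops at preterm birth, and the protocol's rationale (Section 2) says that a shorter cervix carries a higher risk of preterm birth. The women with truncated series are therefore likely to include those whose cervix shortened most. Losing them would make the cervix look more stable than it was, and would restrict the comparison of B with C to women who did well.

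The second issue is the time scale. The only grid the SAP offers is the visit number. With entry spread over eight weeks, the same visit number means different gestational ages in different women. The protocol's own rationale says that cervical length changes with gestational age, with progressive shortening after week 30.

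**Working it through.** **1. Reproducing the eight visits.** Take the longest interval allowed (4 weeks) up to 28 weeks, put a visit at 28 weeks when the next step would pass it, and use 2 weeks afterwards.

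| Entry (weeks) | Scheduled visits (weeks) | 36-week visit is final | Separate visit at 36 6/7 |
|---|---|---|---|
| 16 | 16, 20, 24, 28, 30, 32, 34, 36 | 8 | 9 |
| 20 | 20, 24, 28, 30, 32, 34, 36 | 7 | 8 |
| 24 | 24, 28, 30, 32, 34, 36 | 6 | 7 |

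Entry at 16 weeks reproduces the SAP's 8 if the 36-week visit is the final one. On either count a woman entering at 24 weeks has two fewer visits than one entering at 16, and fewer than 8. If entry were uniform over the 57 days from 16 0/7 to 24 0/7 (an assumption), and the 36-week visit were final, the 28 entry days before 20 0/7 would give 8 visits: 28/57 = 49% of women.

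**2. What a visit number covers** (same schedule, entry from 16 to 24 weeks).

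| Visit | Gestational age (weeks) |
|---|---|
| 2 | 20 to 28 |
| 3 | 24 to 30 |
| 4 | 28 to 32 |
| 5 | 30 to 34 |
| 6 | 32 to 36 |

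Time since baseline varies too. At Visit 4 it is 28 − 16 = 12 weeks, 30 − 20 = 10 weeks or 32 − 24 = 8 weeks for entry at 16, 20 or 24. A change from baseline at Visit 4 therefore averages over different lengths of follow-up.

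**3. Who would be lost under a complete-series rule.** A woman delivering at 32 weeks has 5, 4 or 3 visits before birth (entry at 16, 20 or 24). One delivering at 34 weeks has 6, 5 or 4. None has a full series. The documents give no expected rate of delivery before 34 weeks for this trial. Over an assumed range of 5% to 44%, the women left per arm of 90 run from 90 × 0.95 ≈ 86 down to 90 × 0.56 ≈ 50, before any loss from late entry.

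**4. Possible effect on the estimate (illustration only).** None of these inputs is in the documents. All women enter at 20 weeks. A share p delivers before 34 weeks, spread evenly over 26 to 34 weeks. The cervix shortens by 1.0 mm/week in those women and 0.3 mm/week in the others. The quantity is mean shortening from 20 to 28 weeks.

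- Complete series only: 8 × 0.3 = 2.4 mm, whatever p is.
- Women still pregnant at 28 weeks: of the early deliverers, (34 − 28)/(34 − 26) = 0.75 remain, so their share is q = 0.75p/(1 − 0.25p), and shortening is 2.4 + 8 × (1.0 − 0.3) × q = 2.4 + 5.6q.

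| p | q | Still pregnant at 28 weeks (mm) | Complete series (mm) | Understated by |
|---|---|---|---|---|
| 5% | 0.038 | 2.61 | 2.40 | 0.21 mm (8%) |
| 10% | 0.077 | 2.83 | 2.40 | 0.43 mm (15%) |
| 15% | 0.117 | 3.05 | 2.40 | 0.65 mm (21%) |
| 30% | 0.243 | 3.76 | 2.40 | 1.36 mm (36%) |

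For B against C: with p = 30% in one arm and 15% in the other, the difference is 3.76 − 3.05 = 0.71 mm among women still pregnant at 28 weeks and 0 mm among complete series. With 10% and 5% it is 2.83 − 2.61 = 0.22 mm against 0 mm. If p were equal in both arms, this model would give no difference by either route.

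**The case against.** The strongest reply is that the SAP never says it will analyse complete series. A reader might infer from the name of the method that early deliverers are excluded, but the documents do not support that as a statement of fact. Type III tests and least-squares means are also available from a mixed model that keeps partial series, and the SAP names SAS without a procedure. The population definitions in SAP Section 6 lean the other way: the per-protocol set keeps women followed to the end of pregnancy, and the intention-to-treat set needs only one visit after the first. This reply stands against a flat claim of exclusion. It does not close the gap, because membership of a population decides who enters the data set, and the procedure can still discard an incomplete row.

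A reader might also conclude that the protocol's schedule contradicts the SAP's eight visits. It does not. Eight is exactly right for entry at 16 weeks with week 36 as the final visit, and the protocol allows more frequent visits before 28 weeks. What stands is that no single number fits every entry age under this schedule.

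Protocol 7.2.2 frames these outcomes as before versus after insertion. Protocol 5.4.2 places the post-insertion scan at visit two at the latest and plans the paired angle and length measurement in 60% of pessary women, about 54 of 90 per arm. For that immediate contrast later delivery matters little, unless a complete-series method is applied to the whole series. The SAP nevertheless extends the analysis over time and schedules scans at every visit, so this narrows the point without removing it.

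Finally, B and C are randomised, so the mixing of gestational ages is balanced between them in expectation. It adds noise to that comparison and does not by itself bias it. Its main harm is to the description of within-woman change.

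**Conclusion.** The point holds as a gap in specification with a foreseeable consequence. SAP Section 10 names a repeated-measures ANOVA and leaves open the time scale and the treatment of incomplete series. Series will be incomplete for reasons linked to the outcome (early delivery) and by design (late entry). Visit numbers span from 4 to 8 weeks of gestational age for Visits 2 to 6 under the schedule above.

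Understated shortening is conditional on two things: that the classical form is used, and that women with faster shortening deliver earlier. The second is plausible from the protocol's rationale, but no shortening rates are given. The millimetre figures above show direction and mechanism under assumed values. They are not estimates for this trial, and it would be wrong to read them as a known bias.

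The outcome is secondary, in a study both documents call exploratory. The primary comparison of spontaneous preterm delivery is unaffected. The change is worth making because it is cheap, and because in an open-label study the choice of model should not be left until the data have been seen.

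**What to change.** Replace the ANOVA in SAP Section 10 with a linear mixed model, along these lines:

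> Cervical length and cervical angle in groups B and C will each be analysed by a linear mixed model using all available post-baseline measurements. Fixed effects are baseline value, arm, gestational age at measurement and arm by gestational age. Within-woman correlation is modelled by a random intercept and slope, or by a spatial covariance. No woman is excluded because later measurements are missing.

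Three details should be settled with it:

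- **Covariance.** Scan times vary from woman to woman, so an unstructured covariance is generally not estimable on this time scale. It is an option only if scans are grouped into stated gestational-age windows.
- **Time scale.** Say which dating of gestational age is used, since SAP Section 10 lists two. Allow for curvature if needed, as the protocol describes progressive shortening after week 30.
- **Interpretation.** State that anything the model implies beyond a woman's delivery rests on a missing-at-random assumption, that results are to be read as describing women still pregnant at the gestational age concerned, and how many women contribute at each age.

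Redefining how many visits count as required would not repair this analysis, because it touches only the per-protocol definition.

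The cost is a paragraph of SAP text and somewhat more modelling work, with a missing-at-random assumption that must be stated. No new data are needed.

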#### 5.5. Placement and repositioning of the cerclage pessary containing sustained-release progesterone

Once the cervix length and positioning have been examined by transvaginal ultrasound, and any vaginal infection has been ruled out or treated, the progesterone pessary should be implanted by a professional qualified and trained for that purpose. For placement, the participant must be lying in supine position.

The removal of the pessary will be done by vaginal examination at week 36 6/7 or earlier, if there is any medical indication for induction of premature labor or elective cesarean section. The pessary will also be removed from participants in preterm birth labor not responding to treatment with tocolytics.

During controls or visits to emergency departments or medical offices, participants who report vaginal discharge should be examined by a physician to rule out infection by relevant testing (vaginal discharge smears for PCR), and deliver the appropriate treatment without the need to remove the pessary. This condition will be considered an adverse event.

In the event that the medicated cerclage pessary is spontaneously expelled it, will be repositioned within maximum 72 hours; if this does not occur, the patient will be withdrawn from the study but considered in the final statistical analysis under the intention-to-treat principle.

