#### **Definition of Adverse Drug Reactions**

An Adverse Drug Reaction is any harmful and undesirable response to an Investigational Medicinal Product (IMP) or drug, regardless of the dose administered.

All adverse events reported by subjects spontaneously at any time point should also be documented.

All adverse events should be documented in the CRF with the following information according to the case:

- Description (adverse events reported within the term)
- Start date
- End date or continuation
- Whether the adverse event was serious
- Severity

- Outcome
- Mitigation actions
- Causal relationship with the IMP
- Definition of severity

The clinical severity of an adverse event will be classified as:

Mild:	The signs and symptoms can be easily tolerated. Symptoms may be ignored and disappear when the subject is distracted.
Moderate	Symptoms cause discomfort but are tolerable, not ignorable, impairing concentration ability
Severe	Symptoms affecting daily life activities.

For adverse events where intensity changes over time, the maximum intensity observed throughout the adverse event will be documented.

Adverse events that occur during the enrollment period, but prior to the first administration of the IMP and worsen during or after administration of the IMP will be documented as new adverse events.

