Evaluation of the Pessary's Adhesion (Groups B and C)		X	X	X	X	X	X	X
Treatment Compliance (Group A)		X	X	X	X	X	X	X
Adverse Events	X	X	X	X	X	X	X	X
Subject's Evaluation		X	X	X	X	X	X	X
Birth ⁴								X

1. Pulse and Temperature are added

2. Confirmatory

3. Smear

4. Birth Characteristics: Medication (corticosteroids, antibiotics, tocolysis), hospital admissions; Delivery (Home, Via, interruption); Newborn baby (gender, weight, size, gestational age, head circumference, weight EG, Apgar score); Neonatal complications (infection, respiratory distress syndrome, Intraventricular hemorrhage, Necrotizing Enterocolitis, retinopathy, Blood Transfusion, other); Interventions; Conditions at discharge.

The statistical analysis will be made with SAS software, version 9.2 or greater.

DATABASE MANAGEMENT

The data will be attached to the statistical report. The subjects that will not participate in the analysis (subjects that only completed baseline) will not be included in the tables and figures but they will be included in the listings of data.

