11. SAFETY ANALYSIS

11.1 ADVERSE EVENTS

The evaluation of adverse events (AE) will be monitored throughout the study, by direct observation at each visit.

All AE will be recorded (according to the definition), and not only those where the investigator suspects a causal relationship with the treatment. Adverse events of interest; i.e., those in which the investigator at each site must pay particular attention are those that have been defined as local safety (pain, irritation, itching and infection) and major maternal complications attributable to the pessary as chorioamnionitis, severe vaginal or cervical trauma.

All the AE will be encoded in MedDRA version 19.1 or higher to be summarized by System Organ Class (SOC) / Preferred Term (PT).

The following 3 overview tables will be generated by treatment group and overall:

1) Summary of the number and percentage of subjects with at least 1:

- AE
- Serious AE
- Non-serious AE
- Unexpected AE
- Severe AE
- Related AE
- Related serious AE
- AE leading to discontinuation from IMP

The percentage denominator will be the number of subjects in the safety analysis.

2) Summary presenting the number of AEs per subject categorized as 0, 1, 2, 3, 4, 5, and >5;

3) Summary of the number and percentage of AEs for:

- AEs
- Serious AEs
- Non-serious AEs
- Unexpected AEs
- Related AEs
- Related serious AEs
- AEs leading to discontinuation from IMP

The percentage denominator will be the total number of AEs.

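### Local-safety symptoms are looked for partly unequally by arm: the pain questionnaire and the removal examination are pessary-only, and the SAP does not say whether what they find enters the by-group adverse event tables

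*SAP*

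**What the plan says.** **Common to all three groups.** Protocol 5.4.3 has possible side effects recorded at control visits in every treatment group. Table 1 in SAP 5 lists adverse events at every visit. SAP 11.1 tells investigators to watch particularly for "those that have been defined as local safety (pain, irritation, itching and infection"), with no restriction by group. Protocol 8 adds "All adverse events reported by subjects spontaneously at any time point should also be documented". The row "Gynecological Exam" in Table 1 is marked at Visit 1 only, for all arms.

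**Pessary groups only.** SAP 10 heads the questionnaire "Acceptability and tolerability of insertion (only groups B and C"). It includes pain at insertion, the "Visual Analog Scale of pain (VAS) (visit 1 and final visit"), and an item on intercourse with the pessary that has a pain category. Protocol 7.2.3.2 likewise ties the pain outcome to inserting and using the pessary. Protocol 5.5 states "The removal of the pessary will be done by vaginal examination at week 36 6/7 or earlier". Table 1 also has a row "Evaluation of the Pessary's Adhesion (Groups B and C").

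**Reporting.** SAP 11.1 and 11.2 tabulate adverse events by treatment group. Neither section says how a questionnaire answer or a removal finding is handled.

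**The concern.** Local safety is a stated objective in both documents, and the capsule group is the only reference for what women using vaginal progesterone report without a device. The by-group tables put that reference beside the two pessary columns. If some pessary-arm events come from a structured pain question or a scheduled examination that capsule women do not have, part of any difference reflects how hard each arm was looked at. The trial is open-label, so nothing offsets this. Afterwards, a true device effect on pain or on vaginal or cervical findings could not be separated from a difference in detection.

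Infection and discharge are outside this point, because SAP 10 has discharge asked about at every control visit without limiting it to the pessary groups.

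**Working it through.** **Step 1: sources set side by side**

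| Source | Groups | When | What it can detect |
|---|---|---|---|
| Adverse event check (Protocol 5.4.3; SAP Table 1, 11.1) | A, B, C | Every visit | Any event; pain, irritation, itching and infection singled out; no fixed question given |
| Gynecological examination (SAP Table 1) | A, B, C | Visit 1 only | Vaginal and cervical findings at baseline |
| Pessary row of Table 1, read with SAP 9 | B, C | Visit 2 to final | Described only as a record of whether removal was needed |
| Questionnaire and pain scale (SAP 10) | B, C by heading | Visit 1 and final visit | Pain; no irritation or itching item |
| Examination at removal (Protocol 5.5) | B, C | Removal | Vaginal and cervical findings |

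The last two rows are the asymmetry. It concerns pain and findings seen on examination. The questionnaire cannot raise irritation or itching rates, because it does not ask about them.

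**Step 2: a contradiction within SAP 10.** The questionnaire is limited to B and C, yet the paragraph on the pain scale ends "These comparisons will be made amongst all treatment groups". The cervical-measurement paragraph just before it uses the same sentence but restricts it to the pessary groups. As written, the SAP leaves open whether capsule women complete the scale.

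**Step 3: illustration of size.** The documents give no local-symptom rate and no capture rate, so there is no plan figure to reproduce. Protocol 9.1 supplies 90 women per group. Everything else here is assumed:

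- the same true risk in both arms, t = 0.20;
- capture of 0.90 in a pessary arm;
- capture c of 0.50 to 0.80 in the capsule arm;
- pessary-only findings do enter the adverse event data.

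Observed rate = t × capture. Observed rate ratio = 0.90 / c. The false-positive rate is the exact probability, from two binomials with n = 90 each, that a two-sided uncorrected chi-square test gives p ≤ 0.05.

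| Capsule capture c | Pessary observed | Capsule observed | Ratio | False positive |
|---|---|---|---|---|
| 0.90 (equal) | 18% | 18% | 1.00 | 4.9% |
| 0.80 | 18% | 16% | 1.13 | 6.3% |
| 0.70 | 18% | 14% | 1.29 | 11.0% |
| 0.60 | 18% | 12% | 1.50 | 20.0% |
| 0.50 | 18% | 10% | 1.80 | 33.8% |

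Hand check of the last row: the pooled rate is 0.14. The null standard error is √(0.14 × 0.86 × 2/90) = 0.0517. The standard error under the observed rates is √((0.18 × 0.82 + 0.10 × 0.90)/90) = 0.0514. Then (0.08 − 1.96 × 0.0517)/0.0514 = −0.42, which gives about 34%.

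**Step 4: sensitivity to the true risk.** Over the same capture range of 0.80 down to 0.50, the false-positive rate runs from 5.6% to 17.4% at t = 0.10 and from 7.4% to 50.7% at t = 0.30. Fisher's exact test is lower: 15.2% at t = 0.20 and c = 0.60, against 20.0% for chi-square.

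**The case against.** The strongest reply is that the plan already looks for local symptoms in every arm. That is largely right. A reader might infer that pain is actively sought only in the pessary arms and merely volunteered in the capsule arm. The documents do not support this: the visit-by-visit check, with local symptoms singled out, covers all three groups, and the provision on spontaneous reports is additional and applies to everyone. What the common check lacks is a fixed question, so the pessary questionnaire is still an extra prompt.

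A reader might also take the pessary row of Table 1 as a genital examination at each later visit. SAP 9 describes only a record of whether removal was needed, so it is not counted here. The Visit 1 gynecological examination is equally limited in all arms, which leaves removal as the one extra scheduled vaginal examination. Table 1 lists transvaginal ultrasound at every visit, although Protocol 5.4.3 makes it discretionary for capsule women; its stated purpose there is to measure cervical length.

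Three further replies carry weight. First, the questionnaire is an acceptability outcome summarised in SAP 10, and no text turns its answers into adverse events. Equally, no text keeps them out, and SAP 11.1 wants all adverse events recorded. Second, the safety objective concerns women using the pessary, Protocol 4 makes women their own controls for local safety, and the adverse event test in Protocol 9.2 compares doses, most naturally B with C, where ascertainment is the same. The plan therefore does not clearly specify a pessary-versus-capsule test of local events, but the by-group tables still invite that comparison. Third, insertion pain and intercourse with a pessary have no capsule counterpart, so restricting those items is inherent in the design and is not a fault.

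**Conclusion.** The point holds in a limited form. Ascertainment of pain and of vaginal or cervical findings is partly unequal by arm, and the SAP does not say whether pessary-only findings feed the by-group tables. If they do, those rates may be raised in the pessary groups relative to capsules. It would go too far to say that the rates are biased, or that the distortion is large: both depend on an unstated data flow and on capture rates that nobody has given.

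On the assumptions in the working at 20% true risk, the apparent ratio is about 1.1 to 1.8 and the false-positive rate about 6% to 34%. At the mild end the effect is negligible. This is an inexpensive improvement to make and does not threaten the primary analysis. The conflict within SAP 10 over who is compared on the pain scale stands regardless of these assumptions.

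**What to change.** 1. Within the adverse event check already scheduled at every visit, ask all women the same fixed question on vaginal or pelvic pain, irritation and itching. In SAP 11, base the by-arm local-safety comparison on that common source.
2. Add a source field to the adverse event record. Report events found only through the pessary questionnaire or the removal examination in a separate table for groups B and C, outside the comparison with group A.
3. In SAP 10, state which groups complete the pain scale, and make the heading and the comparison sentence agree.

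The cost is one line on the visit form, one data field and SAP wording; no procedure is added. Item 1 changes data collection, so it may need an amendment, with ethics approval under Protocol 12 if it is judged substantial. Item 3 and the separate table in item 2 need only SAP wording, and the table remains possible after data collection wherever the source of an event can be identified. The downside is that some minor pessary findings leave the headline arm comparison.
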